The study team has established proof of concept for a brief checklist to be used by older patients and their companions in the waiting room prior to medical visits. The checklist is designed to elicit and align patient and companion perspectives regarding patient health issues to discuss with the doctor, and to stimulate discussion about the companion's role in the visit. The premise for the checklist is that companions are typically motivated to support patients during medical visits, but that they often lack knowledge of the patient's health concerns and preferences for communication assistance. In a proof of concept randomized study of 32 patient-companion dyads, we found that the checklist was highly endorsed by patients, companions, and doctors. Analyses of audiotaped medical visits indicated that communication was significantly more patient-centered among patient-companion dyads who completed the checklist as compared with those who received usual care, and did not receive the checklist.(33) In post-visit surveys, doctors were 34% more likely to agree that intervention versus usual care companions "helped them provide good care to the patient" (94.1% vs. 60.0%; p=0.02). Intervention patients were more likely than usual care patients to agree that because their companion was present they "better understood their doctor's advice and explanations" (82.4% vs. 46.7%; p=0.03). However, *older adults with moderate and severe cognitive impairment were excluded in this early phase study.* Therefore, building on our preliminary work, this study seeks to refine and test the checklist to address the communication needs of older adults across a range of mild, moderate, and severe cognitive impairment.

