## Study Aims

This study includes two specific Aims. The work associated with Specific Aim 1 was previously undertaken through a complementary study which was separately approved under IRB protocol 6194 ((34)). Although we restate the two specific Aims of this project for the sake of comprehensiveness, this proposal seeks approval for the work that pertains to Specific Aim 2.

**Aim 1. To refine a patient-companion checklist to address the communication needs of cognitively impaired older adults during primary care visits.** We will undertake an iterative user-centered design process to incorporate patient and companion feedback regarding checklist content and alternative delivery characteristics (optimal timing of delivery prior to the medical visit; whether the checklist is self-administered versus delivered by a facilitator) by undertaking in-depth interviews with older patients with mild, moderate, or severe cognitive impairment (n=20) and their companions (n=20; 20 dyads in total).

**Aim 2. To evaluate the feasibility of delivering the refined checklist to patients with cognitive impairment and their companions and to compare the checklist and control protocol with respect to patient centered communication (from visit audiotapes).** We will conduct a two-group pilot randomized trial to examine feasibility of the protocol and to compare medical communication during visits of patient-companion dyads who complete the checklist (n=50) with patient-companion dyads who receive usual care (n=50).

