The primary outcome of the Aim 2 trial is an objective composite measure of visit medical communication that will be constructed from RIAS-coded categories. This outcome, *patient-centered communication*, is a ratio of statements that encompass psychosocial and socio-emotional elements of medical dialogue that reflect the lived experience of patients (in the numerator), in relation to statements that are more biomedical and disease-focused (in the denominator).(23, 40) Higher values ( $>1$ ) indicate more patient-centered encounters and lower values ( $<1$ ) indicate more doctor-centered encounters. Prior work indicates the measure has predictive and concurrent validity in relation to consequential patient and doctor outcomes.(23, 40, 44, 45) We will additionally examine several secondary outcomes of visit processes (e.g., visit duration and verbal activity of patients, companions, and doctors, from audiotapes) and *discussion of memory* from audiotapes. Acceptability will be evaluated from responses to the agenda setting checklist by intervention dyads. Measures of patient-companion concordance will be constructed to indicate whether each health issue was selected as a priority by the patient only, companion only, neither, or both. From companion responses to post-visit surveys we will assess how the checklist was completed (patient only, companion only, together) and how long it took to complete the checklist. The utility, burden, and helpfulness of the checklist will be assessed in written post-visit surveys using questions from our formative work. (33) Additional measures. From patients' electronic health record we will assess age, gender, and diagnosis of cognitive impairment or dementia at the time of the enrollment visit. Cognitive function will be measured using the Mini-Mental State Examination (MMSE)(41) which will be administered to patients by research staff immediately after the enrollment visit. From telephone interviews we will assess patient race/ethnicity, living arrangement, educational attainment, receipt of help with self-care and household activities, and numbers of daily prescribed medications. Measures of companion characteristics will include relationship to the patient, gender, self-rated health, and educational attainment, from

follow-up telephone interviews. We will assess clinician characteristics (age, gender, specialty training, and years in practice) from baseline surveys administered at the time of informed consent.

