## Analysis

Analyses will be performed in SAS statistical software, with each patient-companion dyad and their recorded visit as the unit of analysis. In this two-group randomized pilot trial, we will compare the effects of the refined checklist on medical communication among up to 100 (50 per group) patients ages 65+ with cognitive impairment and their companion. Simple statistics (frequency distributions, group means) will be used to assess potential differences between eligible patients willing and unwilling to participate, between enrolled participants assigned to intervention and control groups, and process measures relating to completion of the agenda setting intervention. We will rely on established cut-points and approaches to constructing primary and secondary outcome measures, as well as measures of patient and companion attributes that will serve as control variables (socio-demographic characteristics, health status, aspects of the patient and companion relationship). We will rely on established cut-points of the Mini-Mental State Examination test to categorize patient participants as having mild (scores of 20-25), moderate (scores of 10-20) or severe (scores of less than 10) cognitive impairment.(41, 42) We will primarily evaluate the consistency, direction, and magnitude of differences in study outcomes by undertaking analyses that are stratified by intervention group (checklist versus usual care) and for the subgroups of patient cognitive function (mild, moderate, or severe, based on the Mini-Mental State Examination cut-points). Intervention effects on primary and secondary outcomes will be examined using regression models in which the main independent variable is treatment assignment. We will use generalized estimating equations (PROC GENMOD in SAS, version 9.4 (SAS Institute, Cary North Carolina)) to assess the direction, magnitude, and statistical significance of between-group differences in outcomes. The generalized estimating equations method will be used because it accounts for within-clinician clustering of patients and the different numbers of enrolled patient-companion dyads per clinician.(46) An exchangeable correlation structure will be assumed. Regression models will include treatment assignment (agenda setting versus usual care) and patient-level covariates that are postulated as affecting communication, such as age, gender, and cognitive function. We will evaluate recruitment, retention, and the timeliness and completeness of collected data,(47) as well as checklist acceptability (utility, burden, helpfulness) using questions from our formative work. (33) The statistical significance of patient-companion concordance/discordance on priorities for the visit agenda will be assessed with McNemar's test. We recognize the need for caution in interpreting pilot trial results. We will evaluate recruitment and dropout rate as well as effect size of primary and secondary outcomes to help inform the design and sample size calculations for a larger trial. We will examine similarities and differences in pilot trial results and our initial proof-of-concept study. The ultimate goal of the Aim 2 pilot trial is to demonstrate the feasibility of implementing the study protocol among primary care patients with a range of cognitive impairment and their companion and to glean insight regarding effects of the refined checklist for medical communication.

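### McNemar's test, named for patient-companion concordance, compares how often each selects an issue; no estimate of how far they agree is planned

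*Combined protocol and SAP*

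**What the plan says.** The Measurement section defines concordance issue by issue, as "whether each health issue was selected as a priority by the patient only, companion only, neither, or both". The data come from the checklist, which only the intervention arm receives; the same section refers to "Acceptability will be evaluated from responses to the agenda setting checklist by intervention dyads". It adds that companions will report whether the patient, the companion or both together filled it in.

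The Analysis section takes the dyad as its unit and gives one inferential method for this measure: "The statistical significance of patient-companion concordance/discordance on priorities for the visit agenda will be assessed with McNemar's test". It states no null hypothesis and does not say which version of the test will be used. It separately plans simple descriptive statistics for "process measures relating to completion of the agenda setting intervention", without saying whether these include the concordance measure. No agreement coefficient, percent agreement or confidence interval for agreement is named anywhere in the document.

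The Background gives the context: "The checklist is designed to elicit and align patient and companion perspectives".

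**The concern.** The label and the test do not fully match. Concordance lies in the cells for both and neither, and those cells do not enter McNemar's statistic. The statistic asks whether patient-only selections are as frequent as companion-only selections, which is the same as asking whether the two parties select the issue at equal rates. That addresses the direction of discordance. It does not address how much concordance there is.

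A report that followed the plan literally could attach a p-value to concordance that carries no information about it. A non-significant result could be read as good agreement, or a significant one as poor agreement, and neither reading would be justified. What is at stake is the interpretation of one process measure: how often patients and companions put the same issues on the agenda.

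**Working it through.** The document gives no figure for this analysis (no expected selection or agreement rates, no power, no number of issues), so there is nothing to reproduce. The check uses assumed tables for a single health issue.

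**Inputs**
- Four cells per issue, from Measurement: a = both, b = patient only, c = companion only, d = neither.
- n = 50 dyads, the planned size of the intervention arm in Study Aims. This is a maximum.
- Two-sided 0.05 as the reference level (assumed). All cell counts are assumed.

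**Formulas**
- Exact McNemar: two-sided binomial on b + c discordant pairs with probability 0.5.
- Chi-square versions: (b − c)²/(b + c) uncorrected; (|b − c| − 1)²/(b + c), floored at 0, with continuity correction.
- Percent agreement: (a + d)/n, with a Wilson 95% CI.
- Kappa: (po − pe)/(1 − pe), where po is observed and pe is chance agreement.
- Positive agreement: 2a/(2a + b + c). Negative agreement: 2d/(2d + b + c).

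**Results**

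| (a, b, c, d) | Agreement | Kappa | Exact McNemar p |
|---|---|---|---|
| (0, 25, 25, 0) | 0% | −1.00 | 1.00 |
| (13, 12, 12, 13) | 52% (38.5 to 65.2%) | 0.04 | 1.00 |
| (22, 3, 3, 22) | 88% (76.2 to 94.4%) | 0.76 | 1.00 |
| (23, 2, 2, 23) | 92% | 0.84 | 1.00 |
| (22, 0, 6, 22) | 88% (76.2 to 94.4%) | 0.76 | 0.031 |
| (12, 19, 6, 13) | 50% | 0.06 | 0.015 |

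**Same agreement, different p.** The two 88% tables each have six discordant pairs. Split 3 vs 3, p=1.00 in all three versions. Split 0 vs 6:
- exact: 2 × 0.5⁶ = 0.031;
- uncorrected: (0 − 6)²/6 = 6.00, p=0.014;
- corrected: (6 − 1)²/6 = 4.17, p=0.041.

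The small p here is the test working properly. Selection rates are 22/50 = 44% for patients and 28/50 = 56% for companions.

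**Different agreement, same p.** The first four rows run from no agreement to 92%, and all give p=1.00, because b = c in each.

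**Why percent agreement is not enough alone.** Suppose each party independently selects an issue 10% of the time (assumed). Then:
- raw agreement by chance = 0.1 × 0.1 + 0.9 × 0.9 = 82%;
- kappa = 0;
- positive agreement = 2 × 0.01/(2 × 0.01 + 0.09 + 0.09) = 0.02/0.20 = 10%;
- negative agreement = 2 × 0.81/(2 × 0.81 + 0.09 + 0.09) = 1.62/1.80 = 90%.

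The 82% comes almost entirely from the neither cell. Positive agreement and kappa expose this; raw agreement does not.

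**The case against.** The strongest reply is that McNemar's test is a valid paired test and that the plan's phrase covers discordance as well as concordance. Whether companions raise issues that patients do not, or the reverse, is a sensible question, and the patient-only and companion-only cells are the right ones to compare. This stands. A reader might infer that the test is wrong and should be dropped; the documents do not support that. The fault is limited to the concordance half of the label.

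Second, the four-cell measure is already planned, percent agreement follows from it by addition, and descriptive statistics are planned for process measures. This stands in part. The data will exist, but the plan does not say that the descriptive statistics include concordance, and it names no agreement summary or interval.

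Third, a reader might take the Background wording on aligning perspectives to mean that agreement is a trial objective, or that a high figure would show the checklist aligned the two. Neither follows. Alignment is described as the checklist's purpose; it is not an Aim 2 objective or a listed primary or secondary outcome. Checklist responses come from intervention dyads only, with no control-arm or before-and-after comparison.

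Fourth, the tables are constructed. They show that the p-value and the agreement are different quantities, not that this trial is likely to reach a wrong conclusion.

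**Conclusion.** The point holds as a minor mismatch between label and method, together with a missing agreement summary. That McNemar's p-value ignores the concordant cells is a property of the statistic and needs no assumption. The sizes shown rest on assumed cell counts in 50 dyads; with fewer dyads the agreement intervals would be wider.

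The consequence is confined to one process analysis in one arm of a pilot whose Analysis section already urges caution in interpreting results. The primary outcome, patient-centered communication, and the GEE comparisons between arms are unaffected.

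One further limit applies to any agreement figure. Where one person filled in the checklist, or the two did so together, the cells may not reflect two separate choices.

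**What to change.** Amend the Analysis section in a few sentences:
- For each health issue, report the four-cell distribution and percent agreement with a 95% CI.
- Report positive and negative agreement, or kappa, alongside it. This should be required, because raw agreement is inflated when an issue is rarely selected.
- Keep McNemar's test only as a labelled comparison of patient and companion selection rates, and state which version is used.
- Present the agreement results with regard to how the checklist was completed (patient only, companion only, together), and describe them as descriptive of intervention dyads, not as evidence that the checklist produced alignment.

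No new data are needed; the four cells and the mode of completion are already to be collected. The cost is a few more lines of analysis and reporting per issue. The intervals will also be wide with at most 50 dyads: about 18 percentage points at 88% agreement (94.4 − 76.2) and 27 at 52% (65.2 − 38.5), and wider still if the results are split by how the checklist was completed.
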